6.2.2.4 Late apnoea

Any documented significant apnoea occurring in NICU or other hospital ward within 24 hours of completion of surgery, excluding early apnoeas.

6.2.3 Other outcomes relating to anaesthesia group:

- Success rate of nerve block
- Time taken for nerve block
- Behaviour of child during nerve block, during surgery and in PACU
- Time to first feeding

6.2.4. Incidental outcomes not related to choice of anaesthesia:

• Incidence of hernia recurrence at 2 years will be recorded. If the repair was unilateral the incidence of contralateral occurrence will be noted.

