3. STUDY DESIGN

3.1 Experimental Design: Prospective, observer blind, multi-site, randomised, controlled, equivalence trial

3.2 Randomisation: Randomisation to either of the two treatment groups (GA or RA) will be by block and stratified by site and gestational age at birth. Gestational age at birth strata will be:

- 26 weeks to 29 weeks and 6 days
- 30 weeks to 36 weeks and 6 days
- 37 weeks and more

Access to randomisation numbers will be via a 24 hour web-based randomisation service set up and maintained by A/[name] at The Data Management & Analysis Centre, Department of Public Health, University of Adelaide, South Australia: http://www.dmac.adelaide.edu.au/gasRandomisation

Entry to the website is password protected.

3.3 Blinding: The anaesthetist will be aware of the group allocation. The psychologist and paediatrician performing the 2 and 5 year neurodevelopmental assessments will be blinded to study group. Parents will not be told which group their child was in but they will be allowed to discover the group and will be told if asked. Parents will be clearly instructed that if they do discover the group then they should not inform the assessing psychologist. A record will be made of whether or not the parents or the psychologist became aware of the allocation. The apnoea assessment and recovery assessment will not be blinded.

3.4 Study duration: The duration of subject participation is five years.

- Children will be enrolled before surgery.
- Data will be collected before and during anaesthesia and in the early postoperative period.
- Formal neurodevelopmental assessment will occur at 2 and 5 years corrected age (see appendix 1 for definition of corrected age).

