3.5.9 Post PACU details

For the 12 hours after PACU or up until routine discharge the following data will be collected.

Details of monitoring for apnoea Drugs given Details of any intervention for apnoea or respiratory support needed Number of significant apnoeas Presence of stridor Time child discharged home

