3.6 Details of apnoea data collection

At all sites heart rate, respiration and oxygen saturation will be continuously recorded in PACU. This data may be downloaded electronically. Details of any intervention for apnoea in PACU will be recorded. An activity sheet will be completed to identify feeding and other activity that may contribute to artefact when data is electronically collected.

After PACU all sites will monitor for apnoea using their established practices. For all patients any post-PACU intervention or change in management due to apnoea will be recorded. After PACU some children will have continuous monitoring with heart rate oxygen saturation oximetry and respiratory rate for up to 24 hours. This data may be recorded and downloaded electronically. As for PACU electronic data will be accompanied by an activity sheet.

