6.2.2.3 Early apnoea

Any significant apnoea in the PACU or the first 30 minutes of the NICU if PACU is bypassed or in the operating room after completion of surgery, discontinuation of general anaesthesia and removal of laryngeal mask or endo-tracheal tube.

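### Late apnoea is defined to 24 hours after surgery, but the form that counts it stops 12 hours after PACU or at discharge, and the early window has no fixed length

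*Protocol*

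**What the plan says.** **Late apnoea (6.2.2.4).** The definition covers a documented significant apnoea in NICU or another ward "within 24 hours of completion of surgery, excluding early apnoeas".

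**What the post-PACU form collects (3.5.9).** "For the 12 hours after PACU or up until routine discharge the following data will be collected". The list that follows includes "Number of significant apnoeas Presence of stridor": a count of apnoeas, with no time for each. The next form (3.5.10, days 1 to 5) asks about medical interventions and readmission but has no apnoea count.

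**Monitoring after PACU (3.6).** "After PACU all sites will monitor for apnoea using their established practices". Also: "After PACU some children will have continuous monitoring with heart rate oxygen saturation oximetry and respiratory rate for up to 24 hours". Those continuous data may be recorded; the text does not require it. The same section has interventions and management changes for apnoea recorded in every patient, with no stated time limit, and 6.2.2.2 records the time of each intervention.

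**Early apnoea (6.2.2.3).** "Any significant apnoea in the PACU or the first 30 minutes of the NICU if PACU is bypassed", plus time in the operating room after surgery once general anaesthesia has stopped and the airway device is out. For children who bypass PACU, the matching form (3.5.8) speaks of 30 minutes on the ward rather than in NICU.

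**Blinding (3.3).** "The apnoea assessment and recovery assessment will not be blinded".

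**Analysis (8.2.2).** There are four apnoea outcomes: early and late, each by vital signs and by intervention.

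**The concern.** An outcome defined over 24 hours needs a record over 24 hours. Here the only routine post-PACU count of significant apnoeas ends at about the middle of that period, or sooner. No analysis plan can restore counts that were not collected, so the mismatch has to be settled in the protocol and its forms.

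The boundary between early and late is set by where the child is, not by the clock. Early and late apnoea are analysed as separate outcomes, so ward logistics decide which outcome an event enters. PACU bypass, length of PACU stay and time of discharge can be influenced by staff who know the allocation.

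Apnoea is in the trial title and is a secondary aim (2.2.2), and the data monitoring committee considers its rate in each group (7.2). The primary IQ analysis is not touched.

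**Working it through.** **Is there a figure to reproduce?** Not for apnoea: the protocol gives no apnoea rate, power, PACU stay or discharge time. Its computed sample size, 598 infants, concerns IQ. It reproduces as 299 per arm (two one-sided t tests, margin 5, SD 15, true difference 1, one-sided alpha 0.025, power 90%) and does not depend on the apnoea windows.

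**Step 1: the late window against the record.** From the protocol: the window ends 24 h after completion of surgery (6.2.2.4); the record ends 12 h after PACU or at routine discharge (3.5.9). Assumed: PACU stay *p* of 0.5, 1 or 2 h, PACU entry at about the end of surgery, and no discharge before the 12 h are up.

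- Record ends at *p* + 12.
- Time not covered = 24 − (*p* + 12) = 12 − *p*.
- Share of the late window covered = 12 / (24 − *p*).

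| PACU stay (h) | Record ends (h) | Not covered (h) | Share covered |
|---|---|---|---|
| 0.5 | 12.5 | 11.5 | 12/23.5 = 51% |
| 1 | 13 | 11 | 12/23 = 52% |
| 2 | 14 | 10 | 12/22 = 55% |

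Earlier discharge shortens the record further. Because the definition is confined to NICU or a hospital ward, an event at home could not count in any case.

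**Step 2: which outcomes are affected.**

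- Late, by vital signs: directly. Beyond the 3.5.9 record there are only the continuous data, in some children, if recorded.
- Late, by intervention: less, because 3.6 sets no time limit.
- Early, both types: not by the 12-hour limit, but by the moving boundary in step 3.

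**Step 3: the early/late boundary.** Take an apnoea 45 minutes after arrival from theatre. In a child still in PACU it is early. In a child who went straight to NICU it is late, because 30 minutes have passed. To show the possible size, assume a constant hazard and a 5% risk over the first 2 h, the same in both arms:

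- hazard *h* = −ln(0.95)/2 = 0.0256 per hour
- risk counted as early = 1 − exp(−*h* × stay in hours)
- 30 min: 1.3%; 60 min: 2.5%; 90 min: 3.8%

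The remainder of the 5% (3.7%, 2.5% and 1.2%) is counted as late. The total does not change; events move from one outcome to the other.

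**Step 4: unequal capture by arm, if it occurred.** Assume a true late risk of 5% in both arms. If one arm's record captures all late events and the other's captures 80% or 60%, the observed risks are 5% against 4% or 3%. The apparent risk ratio is 0.80 or 0.60, and the difference 1 or 2 percentage points, with no true effect. The protocol contains no capture fractions, so this shows direction and scale only.

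**The case against.** Several stronger readings are tempting, and the protocol does not support them.

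- *Late apnoea as a whole is recorded for only 12 hours.* Too broad. Section 3.6 records interventions in all patients without a time limit and allows up to 24 hours of continuous data in some children. The gap falls mainly on one of the four outcomes. It stays open there, because continuous monitoring is neither universal nor necessarily recorded.
- *Unrecorded hours are scored as free of apnoea.* The protocol does not say so. It speaks of documented events, and the scoring of unobserved time may be set in an analysis plan that is not shown.
- *Half the time is missed, so half the events are.* Section 1.4.3 says apnoea is more common in the first 12 hours, so the share of events missed may well be smaller than the share of time.
- *Infants who bypass PACU are at risk for less time in both windows.* A shorter early window lengthens the late one. Only earlier discharge reduces total observation.
- *Early apnoea would differ threefold between arms.* A ratio near 3 (3.8% against 1.3%) needs every infant in one arm to stay 90 minutes and every infant in the other to have the 30-minute window. Nothing in the protocol suggests that.
- *The arms are in fact observed unequally.* Monitoring follows site practice and randomisation is stratified by site, which balances site habits. Section 1.4.4 reports a claim of faster recovery after regional anaesthesia but calls the evidence thin and conflicting. What stands is that stratification does not balance PACU and discharge decisions made with the allocation known.

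Section 3.5.9 also does not say which of its two end points applies when they differ. The working above takes the earlier, which is the natural reading. If the later was meant, children still in hospital would be covered for longer, and the text should say so.

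**Conclusion.** The point holds as a mismatch between definition and data collection in a secondary outcome. Late apnoea by vital signs is defined to 24 hours but is not systematically counted for roughly the last 10 to 11.5 hours, assuming a PACU stay of 0.5 to 2 hours that starts at about the end of surgery, and for longer after earlier discharge. The early window has no fixed length, and the two sections that describe PACU bypass name different places. The same event can therefore be early in one child and late in another.

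Confidence is high for the mismatch, which rests on the text alone. A difference by arm is possible because care and assessment are unblinded, but it is not shown, and its size cannot be estimated from the protocol. It should be corrected.

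**What to change.** Reconcile sections 3.5.8, 3.5.9, 3.6, 6.2.2.3 and 6.2.2.4 so that the outcome window and the collection window are the same.

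- Define early and late by fixed clock times from completion of surgery, identical in both arms and wherever the child is. State how minutes before the airway device is removed are handled in infants under general anaesthesia.
- End the late window where the form ends: either shorten the definition or extend the form. Either resolves the mismatch.
- Add a time field for each significant apnoea. Sections 3.5.8 and 3.5.9 list only a number, and a number cannot be split at a clock time afterwards.
- Treat discharge before the end of the window as end of observation, and report observed hours and monitoring method by arm.
- Keep all randomised children in the main apnoea analysis. Use the continuously monitored children only as a sensitivity analysis, since being monitored is determined after randomisation and selecting on it could itself bias the comparison.

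Cost: wording in five sections and one added form field. If the window is shortened, later events become descriptive; if the form is extended, recording continues for longer in children still in hospital. No sample size changes. This concerns measurement only; how long infants are observed clinically is for the investigators.

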7. SAFETY

7.1 Monitoring during anaesthesia and in PACU

During all nerve blockade there will be ECG, NIBP and pulse oximetry monitoring. During anaesthesia for both groups there will be ECG, NIBP, temperature and pulse oximetry. In the general anaesthesia group there will also be agent analysis and expired CO₂. Blood glucose and haemoglobin will be measured during anaesthesia. In PACU there will be monitoring of oxygen saturation, NIBP, temperature, respiratory rate and heart rate.

7.2 Data monitoring committee

An independent data monitoring committee has been established. The members are as follows.

- Chair: [name] [name], Anaesthetist Sydney
- [name], Neonatologist Sydney
- [name] Statistician Sydney
- [name] Paediatric Anaesthesiologist, Stanford California, USA
- [name] Paediatrician, Sophia Children's Hospital, Rotterdam, Holland

The data monitoring committee will receive interim reports every 6 months. Serious adverse events will be reported to the DMC immediately. Non-serious adverse events will be recorded and reported to the DMC be reported every 6 months. The DMC will report to the Trial Steering Committee.

The DMC will consider the rate of failed awake regional anaesthesia requiring conversion to general anaesthesia and the rate of apnoea in each group. The DMC will also consider all relevant publications and findings from other studies that are relevant to the conduct of this trial.

Codes will only be broken for reports to the Data Monitoring Committee or if requested by the TSC or DMC.

7.3 Adverse events

7.3.1 Adverse events: `An adverse event is any untoward medical occurrence or experience in a patient that occurs following the administration of the trial medication regardless of the dose or causual relationship. The Summaries of Product Characteristics for sevoflurane and bupivacaine or levobupivacaine (appended) list the possible adverse effects of these agents and their expected frequency.

Adverse events are as follows

- Apnoea requiring readmission to hospital within 48 hours of anaesthesia
- Delay in discharge due to apnoea.
- Failure of regional anaesthesia requiring sedation or analgesia (excluding oral glucose)
- Failure of regional anaesthesia requiring conversion to general anaesthesia (from either technical failure of insufficient blockade for length or scale of surgery)
- High neuraxial blockade requiring intubation
- Post-anaesthesia apnoea requiring endo-tracheal intubation
- Delay in extubation for greater than 1 hour after surgery
- Hypoxia during anaesthesia with $SpO_2 < 80$ for 5 minutes
- The administration of vasoactive drugs to support circulation
- Increase in post operative oxygen requirement or increased respiratory support for greater than 1 hour post anaesthesia
- Any other event not mentioned above that results in the child needing medical attention whether or not it is related to the allocated anaesthetic technique or measurement interventions.

Adverse events will be recorded and frequency of AEs will be reported to DMC every 6 months.

7.3.2 Serious Adverse Event: defined as the following regardless of its relationship to trial treatment

- Results in death
- Is life threatening
- Requires hospitalisation or prolongation of existing in-patient hospitalisation
- Results in persistent or significant disability/incapacity
- Is medically important or requires intervention oprevent one of the outcomes listed

Serious adverse events are the following

- Death due entirely or in part to anaesthesia
- Any death within 48 hours of anaesthesia
- Readmission to hospital due to anaesthesia complications apart from apnoea.
- Delay in discharge from hospital due to any complications apart from apnoea.
- Inability to satisfactorily complete surgery, or surgery abandoned due to inadequate anaesthesia (not including surgery successfully completed after conversion of regional to general anaesthesia)
- Evidence of local anaesthesia toxicity such as seizures or arrhythmia
- Any persisting neurological deficit from neuraxial blockade
- Meningitis or epidural abscess within 5 days of anaesthesia
- Evidence for bowel puncture with ilio-inguinal or caudal nerve blockade defined as aspiration of bowel contents
- Barotrauma during general anesthesia resulting in pneumothorax
- Cardiac arrest or bradyarythmia requiring chest compression
- Any other event not mentioned above that is life threatening event or jeopardises the patient or requires medical or surgical intervention to prevent a serious adverse event

SAEs will also be reported to the DMC and all ethics committees involved with the trial.

7.3.3 Suspected Unexpected Serious Adverse Reaction (SUSAR):

Where a serious adverse event is related to study drug and is not noted in the protocol or SmPC of bupivacaine or levobupivacaine and sevoflurane as an expected adverse reaction will be deemed a SUSAR. The Chief Investigator is responsible on behalf of the sponsor to report all SUSAR's directly to the Competent Authority (MHRA) within 7 days of being notified of the event. The Chief Investigator will ensure all SUSAR's are reported to the sponsor, ethics committees and to the co-ordinating centre in Melbourne as soon as possible thereafter.

The Robertson Centre for Biostatistics, University of Glasgow has both web-based and paper reporting systems for SUSARs and this will be used by the UK Chief Investigator to rapidly inform the MHRA, sponsor, ethics committees and coodinating centre in Melbourne.

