AE: Non serious adverse events BCH: Boston Children's Hospital, Boston BRIEF: Behavioural rating of executive function BSID-III: Bayley scales of infant development, version III CPAP: Continuous positive airway pressure CRF: Case report form CSF: Cerebrospinal fluid DMC: Data monitoring committee ECG: Electrocardiograph ESPY: Experimental Delayed Alternation and Spatial Reversal Tasks FLACC: Behavioural scale for scoring postoperative pain in young children measured in 5 areas: face, legs, activity, cry, consolability GA: General anaesthesia GABA: Gamma amino butyric acid HR: Heart rate IV: Intra venous IVH: Intra ventricular haemorrhage NDNMB: Non-depolarizing neuromuscular blocking agent NEPSY: Developmental neuropsychological assessment NIBP: Non invasive blood pressure NICU: Neonatal Intensive Care Unit or Neonatal unit NMDA: n-methyl-d-aspartic acid PACU: Post anaesthesia care unit - also known as the recovery ward PI: Principal investigator PMA: Postmenstrual age (see appendix one) PVL: Peri ventricular leukomalacia RA: Regional anaesthesia RCH: Royal Children's Hospital, Melbourne ROP: Retinopathy of prematurity SAE: Serious adverse events SAR: Serious adverse reaction SUSAR: Suspected unexpected serious adverse events TSC: Trial steering committee UTI: Urinary tract infection WPPSI-III: Wechsler preschool and primary scale of intelligence- Third Edition

SYNOPSIS

Title: A multi-site RCT comparing regional and general anaesthesia for effects on neurodevelopmental outcome and apnoea in infants

Chief investigators: [name] (PI), [name](PI), [name], [name], [name], [name], [name], [name], [name]

Objectives: The primary objective of this trial is to determine whether different types of anaesthesia [regional versus general] given to infants undergoing inguinal hernia repair result in equivalent neurodevelopmental outcomes. Secondary objectives are to describe the frequency and characteristics of apnoea in the post-operative period after both regional and general anaesthesia for inguinal hernia repair in infants, and determine the factors associated with apnoea.

Study population: 660 infants of postmenstrual age 60 weeks age or less, scheduled for inguinal hernia repair under anaesthesia. Exclusion criteria include recognised risk factors for adverse neurodevelopmental outcome or previous exposure to general anaesthesia. Infants born at less than 26 weeks gestation will be excluded.

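### Readmission and delayed discharge for apnoea are serious under the section 7.3.2 definition but non-serious under both event lists, so the protocol gives the same event two reporting routes

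*Protocol*

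**What the plan says.** The abbreviation list at the front of the protocol fixes the vocabulary: "AE: Non serious adverse events".

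Section 7.3.1 then lists AEs. Four entries matter here: "Apnoea requiring readmission to hospital within 48 hours of anaesthesia", delayed discharge because of apnoea, "Post-anaesthesia apnoea requiring endo-tracheal intubation", and high neuraxial block that leads to intubation. The section ends by saying that the frequency of AEs goes to the DMC every six months.

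Section 7.3.2 opens with a definition of a serious event that applies whatever the relation to treatment. One criterion is that the event "Requires hospitalisation or prolongation of existing in-patient hospitalisation". Others cover death, threat to life, lasting disability, and medical importance or the need for intervention to prevent a listed outcome.

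A list of serious events follows. It includes "Readmission to hospital due to anaesthesia complications apart from apnoea" and, in parallel, delayed discharge for complications other than apnoea. It has two death items: death attributable to anaesthesia, and "Any death within 48 hours of anaesthesia". It ends with a catch-all for other events that threaten life or need intervention to avert a serious event.

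On timing, section 7.2 says "Serious adverse events will be reported to the DMC immediately", and "Non-serious adverse events will be recorded and reported to the DMC be reported every 6 months".

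**The concern.** A readmission is a hospitalisation, and a delayed discharge prolongs one. Both meet the section 7.3.2 definition on its face when the cause is apnoea, yet the lists place both among the non-serious events. The definition and the list that follows it are each worded as binding, and no sentence ranks them.

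Two things are at stake. The first is consistency: this is a multi-site trial in several countries, and two sites that both follow the protocol could record the same event differently, which weakens serious-event counts by arm. The second is oversight of individual cases. Reporting to the DMC, reporting to ethics committees and the start of a SUSAR assessment all depend on whether the event is called serious.

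**Working it through.** No arithmetic applies. The check sets each event against the definition, the two lists and the reporting rules.

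| Event | Section 7.3.2 definition | Section 7.3.1 AE list | Section 7.3.2 serious list |
|---|---|---|---|
| Apnoea readmission within 48 hours | Serious (hospitalisation) | Named, so non-serious | Excluded by the apnoea exception |
| Discharge delayed by apnoea | Serious (prolonged stay) | Named, so non-serious | Excluded by the apnoea exception |
| Intubation for apnoea | Serious if judged life-threatening, medically important or a preventive intervention | Named, so non-serious | Not named; perhaps in the catch-all |
| Intubation for high block | As for intubation for apnoea | Named, so non-serious | Not named; perhaps in the catch-all |
| Death after 48 hours, unrelated to anaesthesia | Serious | Not named | Not in either death item |

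**Rows 1 and 2.** The conflict is explicit and needs no clinical judgement. The two lists agree with each other, and both disagree with the definition.

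**Rows 3 and 4.** The apnoea exception is attached only to readmission and delayed discharge, so it does not touch intubation. The catch-all is limited to events not already mentioned. If that means not mentioned in the serious list, it can recover an intubation that meets its terms. If it means not mentioned anywhere in section 7.3, it cannot, because intubation is named in the AE list. The text allows either reading.

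**Row 5.** The definition covers any death, and no death appears among the AEs. The listed items are merely narrower than the definition. Since participation lasts five years (section 3.4), most of follow-up lies outside the 48-hour item.

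**What follows from each classification of rows 1 and 2:**

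- If the definition governs, the event goes to the DMC immediately (section 7.2) and to all ethics committees (section 7.3.2), and it is eligible for SUSAR assessment (section 7.3.3).
- If the lists govern, the event enters a frequency sent to the DMC every six months, so an individual event may wait up to six months. Reporting to ethics committees is stated only for serious events. The SUSAR step starts from a serious event, so it does not begin. Whether any such event would end as a SUSAR is a separate question, because it must also be related to the study drug and unexpected.

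**The case against.** The strongest reply is that the exception is deliberate. The lists are consistent with each other, and apnoea is a pre-specified secondary outcome. Interventions for it are recorded in every infant (sections 3.5.8, 3.5.9, 3.6 and 6.2.2), and section 7.2 tells the DMC to consider apnoea rates by arm. Sparing an anticipated, separately monitored outcome from immediate reporting is a recognisable choice. Much of this stands: apnoea does not escape oversight, and the DMC's review of rates lessens the harm. But the protocol does not say that these events stay serious and are merely exempt from prompt reporting. It classes them as non-serious, against its own definition, and gives no faster route for a single event.

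A reader might infer more than the text supports:

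- *That the gravest consequences of apnoea are reported late.* They are not. Death within 48 hours or due to anaesthesia, and an arrest needing chest compressions, are on the serious list with no apnoea exception.
- *That these events will certainly reach the DMC only every six months.* That follows only where the lists are followed. A site applying the definition reports at once.
- *That intubation is plainly misclassified.* It may meet the definition or the catch-all, but that depends on a clinical reading and on what the catch-all refers back to.
- *That apnoea is the safety event most likely to differ by arm, or the only one the DMC must weigh.* The protocol says neither. Section 11 allows that a difference may be less evident with newer agents, and section 7.2 names failed regional anaesthesia as well.

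**Conclusion.** The point holds for apnoea readmission and apnoea-delayed discharge: the definition and the lists in section 7.3 contradict each other, and sections 7.2 to 7.3.3 attach different reporting to each classification. Intubation for apnoea or high block is ambiguous rather than contradictory. The narrow death items are a minor gap, because the definition already covers any death.

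The size can be stated only in part. The delay to the DMC is at most six months per event, on the assumption that the site follows the lists. The number of events cannot be estimated, since the protocol gives no incidence for them. No delay to ethics committees can be derived, because no deadline is set for that route; the documents show only that an event called non-serious is not stated to reach them. The conclusion assumes nothing beyond the ordinary meaning of hospitalisation and prolonged stay.

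**What to change.** Reconcile the definition, the two lists and the reporting times:

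1. State that the section 7.3.2 definition decides seriousness and that the lists are examples under it.
2. Remove the apnoea exception from the readmission and delayed-discharge items of the serious list.
3. Mark the section 7.3.1 items, including both intubation items, as serious whenever they meet the definition, and make clear what the catch-all refers back to.
4. Replace the two death items with death from any cause.
5. If the sponsor wants expected apnoea exempt from immediate reporting, say so explicitly in sections 7.2 and 7.3, while still classing and counting these events as serious.

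The cost is wording in the protocol and case report form. Without the exemption in step 5 there would be more immediate reports, in a number that the protocol does not allow one to estimate. None of this alters treatment or clinical management.
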